5.8 Adverse events

For all analyses of adverse events (AE), only treatment-emergent AEs will be included. An AE will be considered treatment-emergent in a particular phase if it is worse in severity than the corresponding baseline observation. If the baseline observation is missing, the AE is always considered as treatment-emergent. For ECG, laboratory events, weight changes and hearing loss, only the maximum grade within phase will be reported. For laboratory and weight AEs, a shift from 'abnormally low' at baseline to 'abnormally high' post baseline (or vice versa) is also treatment-emergent. Laboratory AEs starting on day 1 will be considered treatment emergent since it is impossible to know whether the blood samples were taken before or after administration of the first dose of trial treatment and this is the most conservative approach.

SAEs will be analysed as episodes, with all components of the same clinical SAE presented as one episode. Analyses of grade 3 or 4 adverse events will consider each component as separate events. Hearing loss reported in the left and right ear as two separate AEs but with overlapping start and stop dates will be reported in analyses as one AE of bilateral hearing loss at the maximum grade of the two unilateral events.

6 ANALYSIS OF PRIMARY OUTCOMES

6.1 **Primary efficacy analyses**

6.1.1 Modelling technique used in analysis

For the primary efficacy analysis the difference in proportions of favourable outcome between Regimen B (B_{mox} and B_{lev} combined) and Regimen C with corresponding 95% confidence intervals and p-values will be estimated using a stratified analysis of the risk difference from each stratum using Cochran-Mantel-Haenszel weights.⁵ The analysis will be stratified by randomisation protocol and HIV status (as defined in Section 1.6).

6.1.2 Non-inferiority of Regimen C compared to Regimen B at Week 76

Non-inferiority will be shown if the upper bound of the 95% confidence interval of the difference in proportion of favourable outcomes at Week 76 between Regimens B and C is less than the 10% margin of non-inferiority; this must be shown in both the mITT and PP populations. An sensitivity analysis will be undertaken using the mPP population.

6.1.3 Superiority of Regimen C compared to Regimen B at Week 76

If non-inferiority is demonstrated, then superiority of Regimen C compared to Regimen B will be declared if the upper bound of the 95% confidence interval of the difference in proportion of favourable outcomes at Week 76 between Regimens B and C is less than zero,. For this analysis, the mITT population will be primary and the PP and mPP populations will be sensitivity analyses.

Secondary analyses will repeat the primary analysis but compare Regimen B_{lev} and Regimen C, Regimen B_{mox} and Regimen C, and Regimen B and Regimen D, restricting the population in each case to include only concurrent controls within site. For this analysis, the mITT population will be primary and the PP population will be sensitivity analyses. Comparisons of Regimen C and Regimen D were carried out at the time of the primary analysis but considered exploratory.

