Final analysis of STREAM Stage 1, presented at the Union Conference in October 2018, found that 78.8% of participants on Regimen B, the short regimen, had a favourable outcome at 132 weeks from randomisation compared to 79.8% on Regimen A, the 20-24 month long regimen. After adjustment for the randomisation stratification factors of HIV status and centre, the difference in efficacy between the regimens was 1.0%, (95% CI -7.5 to 9.5%) meeting the pre-specified 10% non-inferiority margin. The primary safety outcome of the trial, the proportions of patients who experienced a Grade 3 or greater adverse event at any time during treatment and follow-up, was also similar on the two regimens (48.2% on the shorter regimen compared to 45.4% on the longer regimen).

Bedaquiline is a novel diarylquinoline antibiotic with bactericidal activity. In a phase II trial of patients with MDR-TB time to culture conversion was significantly less in patients receiving bedaquiline compared to those receiving an optimised background regimen only. In December 2012 the US Food and Drug Administration (FDA) approved bedaquiline as part of the treatment regimen for MDR-TB when other agents are unavailable. Stage 2 of STREAM was designed to investigate ways in which Regimen B could be improved either by removing the second-line injectable, which is associated with severe drug toxicity, or by shortening the regimen to 6 months.

In December 2018, the WHO issued revised guidelines for treatment of MDR TB following review of a meta-analysis of available trial and observational data. This included a re-classification of drugs for longer MDR-TB treatment regimens, with moxifloxacin or levofloxacin, bedaquiline and linezolid all listed in Group A (medicines that should be used in the regimen); it was also recommended that when an injectable agent is required, amikacin should be used rather than kanamycin or capreomycin.

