# **6.2 Allocation of treatment (following randomisation)**

In each stage of the trial, patients will be randomised using a web-based randomisation system. Access to the web-based system will be controlled through an authorised username and password. Before treatment allocation the patient's eligibility will need to be confirmed, their site and HIV status, and CD4 count entered into the database. Local laboratory results can be used to determine a patient's HIV status and CD4 count for randomisation, unless central laboratory results are available at the time of randomisation.

Separate randomisation lists for each combination of strata will be prepared in advance, for each site according to whether they are participating in Stage 1 only, Stage 1 and 2, or Stage 2 only, by a statistician independent of the study, using varying block sizes. Should web access not be available at the time of randomisation, a manual alternative using sealed envelopes will be provided.

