## Stage 1 (before Stage 2 begins, or for sites only participating in Stage 1)

Patients will be randomised to Regimen A or Regimen B. Randomisation will be in a 1:2 ratio in favour of Regimen B to allow more data on efficacy and safety to be collected on this regimen. Randomisation will be stratified by (1) site, (2) HIV status for sites with high TB-HIV co-infection rates.

### Stage 2

Prior to the implementation of Version 8.0 of the protocol, in countries where the local NTP has no imminent plans to adopt a short regimen, in keeping with the WHO 2016 MDR-TB guidelines, patients will be randomised to one of four regimens, Regimen A, Regimen B or Regimen C, or Regimen D in a ratio of 1:2:2:2. In countries where the local NTP has adopted or has imminent plans to adopt a short regimen in keeping with the WHO 2016 guidelines and it has been agreed with the STREAM Trial Management Group that randomisation to Regimen A will not be offered, patients will be randomised to one of three regimens (Regimen B, Regimen C or Regimen D) in a ratio of 1:1:1 (see Section 2.1.4). When Version 8.0 of the protocol has been implemented, randomisation to Regimen D will be discontinued as will Regimen A if it has not already been discontinued.

Randomisation will be stratified by (1) site, (2) HIV status & CD4 count status (i.e. three categories: HIV-negative, HIV-positive with low CD4 count of 50 to less than 350 cells/mm^3, or HIV-positive with high CD4 count of more than or equal to 350 cells/mm^3), for all sites.

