For the primary analysis of Stage 2, the difference in favourable outcome rate between Regimen B ( $B_{mox}$  and  $B_{lev}$  combined) and Regimen C with corresponding two-sided 95% confidence interval and p-value will be estimated using a stratified analysis of the risk difference from each stratum using Cochran-Mantel-Haenszel weights. For Regimen C, non-inferiority will be shown if the upper bound of the 95% confidence interval of the difference in proportion of favourable outcomes is less than the 10% margin of non-inferiority; this must be shown in both the mITT and PP populations. The analysis will be stratified by HIV status with three strata: HIV negative, HIV positive with CD4 count between 50 cells/mm³ and less than 350 cells/mm³, and HIV positive with CD4 count more than or equal to 350 cells/mm³.

The secondary non-inferiority outcome at Week 132 for Regimen B compared to Regimen C will be analysed using time to unfavourable outcome, thereby using information on all participants. Data from participants whose scheduled last efficacy visit is before Week 132 will be censored at the time of their last visit, unless they have already become unfavourable. Non-inferiority must be shown in both the mITT and the PP populations. A sensitivity analysis will estimate the proportion unfavourable at Week 132 on the subset of participants randomised at least 132 weeks on or before 30 November

2021. For the superiority comparisons e.g. of Regimen C compared to Regimen B, at Week 76 and Week 132 only the mITT analysis will be considered.

Mortality rates will be calculated for the individual treatment arms and treatment group differences in mortality rates will be calculated together with a 95% confidence interval. In addition, the number of deaths, per-patient years of exposure will be calculated by treatment arm.

Differences in proportions with Grade 3 or greater adverse events will be compared and 95% confidence intervals calculated for overall comparisons, and repeated in subgroups according to HIV infection status and drug resistance patterns.

ECG data for safety analyses for Stage 2 will be from the central cardiology reading facility for the study.

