1.6 Randomisation procedure

Patients were initially randomised to Regimen A, Regimen B, Regimen C, or Regimen D, in a ratio 1:2:2:2, respectively. From protocol version 6.3 onwards randomisation to Regimen A and/or Regimen D were restricted or stopped (Table 1).

Randomisation will be stratified by (1) site, (2) HIV status (split into three strata: HIV negative, HIV positive with CD4 count \geq 350 cells/mm³, and HIV positive with CD4 count < 350 cells/mm³).

Table 1: Randomisation according to protocol version

Protocol version	Allocation ratio	Regimens
6.2	1:2:2:2	A:B:C:D
6.3 or 7.0	1:1:1	B:C:D in countries where the local NTP adopted or has imminent plans to adopt the WHO 2016 short regimen; as for v6.0 elsewhere
8.0 onwards	1:1	B:C

All analyses will be stratified by randomisation protocol to ensure comparisons are made to concurrent controls:

- comparisons of Regimen C to Regimen B will include all participants allocated to these regimens but be stratified by a 3 level variable: v6.2 vs v6.3/7.0 vs 8.0/10.0
- comparisons of Regimen D to Regimen B will be restricted to participants randomised under protocol v6.2/6.3/7.0 and be stratified by a 2 level variable : v6.2 vs v6.3/7.0
- comparisons to Regimen A will be restricted to participants randomised under v6.2 of the protocol

Analyses of the primary endpoint will also be stratified by HIV status as defined above, unless there is insufficient data within strata. If this is the case initially the two HIV positive groups will be combined, but if there is still insufficient data within strata then stratification by randomisation protocol will be prioritised.

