6.2 Tabulation of primary endpoint classification

Since the primary endpoint is a composite of various components, the actual reason (component) for outcome will also be tabulated by treatment arm. Patients will be classified by the first event that made the patient unfavourable (see section 3.2) and further subclassified by whether their outcome is deemed to be bacteriologically related or not, based on a review of all data up to the time that the outcome occurred (see Section 6.2.1).

6.3 **Subgroup analyses**

This primary efficacy analysis will be repeated (in both mITT and PP analysis populations) in subgroups according to the following baseline characteristics:

- HIV infection status
- baseline drug resistance patterns (i.e. resistance to pyrazinamide and isoniazid)
- albumin levels (by severity grade)
- BMI (<16.0 kg/m², 16.0-18.4 kg/m², 18.5-24.9 kg/m², >25 kg/m²)
- cavitation (presence, absence)
- study centre/country
- age (<25, 25-<45, ≥45)

- sex
- Smoking history (current, ex, never)
- Smear grade
- Weight band (<33kg, 33-50kg, >50kg)
- Race.

6.4 **Sensitivity analyses**

The primary efficacy analysis will be repeated:

- A. Unadjusted for any covariates except randomisation protocol.
- B. Adjusted for randomisation stratification factors HIV status and centre. Small strata with fewer than 10 patients will be combined within geographical regions within country.
- C. Adjusted for randomisation stratification factors and any additional important covariate such as cavitation at baseline, baseline bacillary load or adherence.
- D. Ignoring substitutions of levofloxacin for moxifloxicin and vice versa when counting the number of drug substitutions within the definition of unfavourable outcome.
- E. Ignoring starting linezolid alone as a criterion for an unfavourable outcome.
- F. Reclassifying any participants with reinfection (based on genotype or DST) as "non-assessable" rather than unfavourable.
- G. Reclassifying any participants who died as a result of trauma (as adjudicated by independent review) as "non-assessable" rather than unfavourable.
- H. Reclassifying any participants with missing Week 76 culture results because of COVID-19 as "non-assessable" rather than unfavourable.
- Reclassifying any participants with missing Week 76 culture results because of COVID-19 as favourable if they meet the definition of favourable, with the latest of the 2 negative culture results being within the Week 68 window, unfavourable otherwise.

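### Stage 2 randomises within site, but the primary risk-difference analysis leaves site out; if site predicts outcome, the primary confidence interval is modestly conservative.

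*SAP*

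**What the plan says.** SAP Section 1.6 gives the Stage 2 randomisation factors: "Randomisation will be stratified by (1) site, (2) HIV status", the latter in three levels. Protocol Section 6.2 agrees: "Randomisation will be stratified by (1) site, (2) HIV status & CD4 count status", at all sites. It adds that separate lists for each combination of strata are prepared for each site "by a statistician independent of the study, using varying block sizes".

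The primary estimator is a risk difference with Cochran-Mantel-Haenszel weights. In SAP Section 6.1.1, "The analysis will be stratified by randomisation protocol and HIV status". Protocol Section 11.6 names fewer factors for Stage 2: "The analysis will be stratified by HIV status with three strata". Site is in neither list.

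Site does appear elsewhere. Sensitivity analysis B in SAP Section 6.4 is "Adjusted for randomisation stratification factors HIV status and centre", with centres of fewer than 10 patients pooled by region within country. Sensitivity C uses the randomisation factors plus further covariates. Study centre/country is a subgroup factor in Section 6.3. Section 1.6 also has a sparse-data rule: merge the two HIV-positive groups first, then give priority to randomisation protocol. It does not say where site would rank.

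For Stage 1, Protocol Section 11.6 planned a primary analysis stratified by the randomisation factors. Protocol Section 2.1.1 gives the Stage 1 difference "After adjustment for the randomisation stratification factors of HIV status and centre".

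**The concern.** Blocking within site forces the arms to be nearly balanced at each site, so differences in outcome between sites largely cancel from the treatment comparison. An analysis that ignores site still counts that variation as noise. If site predicts outcome, the reported standard error then exceeds the true sampling error and the confidence interval is wider than it need be.

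The primary claim depends on the upper confidence limit lying below 10 points in both the mITT and PP populations, so unneeded width makes non-inferiority a little harder to show. Stage 2 also departs from Stage 1 practice without giving a reason, although a workable site grouping already exists in sensitivity B.

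**Working it through.** **Inputs from the documents.** SAP Section 2.1: favourable rates 0.80 (B) and 0.82 (C), margin 0.10, one-sided 2.5%, 80% power, 172 evaluable per arm, 14% exclusions, 400 enrolled. SAP Table 1: allocation A:B:C:D of 1:2:2:2, then B:C:D of 1:1:1, then B:C of 1:1, so B:C is 1:1 under every protocol version.

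**Input assumed.** The between-site standard deviation *s* of the favourable rate is not given. It is shown from 0 to 15 points.

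**1. Reproduce the plan's figure.** The unpooled two-proportion formula gives 168 per arm. The Farrington-Manning form (variance restricted to the margin) gives 172 per arm, 344 in total, and matches all 12 evaluable totals in Protocol Table 10. Then 344/(1 − 0.14) = 400. Both formulas are unstratified, so the planned power never relied on adjusting for site.

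**2. Standard error with site omitted.** √[(0.80×0.20 + 0.82×0.18)/172] = √(0.3076/172) = 0.0423. The 95% half-width is 1.96 × 0.0423 = 8.29 points.

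**3. Effect of including site.** With p = 0.81, p(1−p) = 0.1539. If blocking balances site exactly and adjustment costs nothing, the true standard error is 0.0423·f, with f = √(1 − s²/0.1539).

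- Excess width of the unadjusted standard error: 1/f − 1
- One-sided error with site omitted: 1 − Φ(1.96/f)
- Power, site omitted: Φ[(0.12 − 1.96×0.0423)/(0.0423f)]
- Power, site included: Φ[0.12/(0.0423f) − 1.96]

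Here 0.12 is the margin plus the assumed 2-point advantage for C.

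| s (points) | SE, site included | SE too wide by | Half-width, site included (points) | One-sided error, site omitted | Power omitted / included (%) |
|---|---|---|---|---|---|
| 0 | 0.0423 | 0% | 8.29 | 0.0250 | 81.0 / 81.0 |
| 5 | 0.0419 | 0.8% | 8.22 | 0.0241 | 81.2 / 81.6 |
| 8 | 0.0414 | 2.1% | 8.11 | 0.0226 | 81.5 / 82.6 |
| 10 | 0.0409 | 3.4% | 8.01 | 0.0213 | 81.8 / 83.5 |
| 15 | 0.0391 | 8.2% | 7.66 | 0.0170 | 82.9 / 86.7 |

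**4. Simulation check.** 344 patients, 8 sites, blocks of 4 or 6 within site and HIV stratum, HIV mix 70/15/15 (site number, blocks and mix all assumed), 3,000 runs. At s = 10 the mean model standard error was 0.0422 against an empirical 0.0408 when stratifying by HIV status alone, and 0.0409 against 0.0407 when stratifying by site. Power was 83.4% and 84.9%. With 15 sites and s = 0, stratifying by site gained nothing (0.0424 against 0.0422). With the true difference at the margin, rejection rates in the 8-site runs at s = 10 were 0.026 with site omitted and 0.030 with site included. Monte Carlo error is about ±0.006, so these runs are too coarse to separate the two.

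**5. How site is added matters.** Simulations of 344 patients with 8 or 13 sites and assumed protocol and HIV mixes show that crossing site fully with three protocol levels and three HIV levels raises the mean standard error (0.0424 to 0.0441 at 8 sites, s = 0) and costs about 2 to 6 points of power, because patients in one-arm strata drop out. Pooled site with HIV status in two levels, or additive adjustment, costs essentially nothing at s = 0 and cuts the standard error by about 2.5% at s = 10.

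**The case against.** The strongest reply has four parts.

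- **Nothing shows that site matters.** No between-site spread is reported, so the cost could be zero. This stands: the point is conditional.
- **The plan loses nothing it counted on.** The 172 per arm is unstratified, and any error is on the cautious side, which in a non-inferiority trial guards against a false claim. This also stands. A reader might infer that the test is underpowered against its stated 80%. The documents do not support that: in the table above, power with site omitted never falls below 81.0%.
- **Site is already handled.** Sensitivity B adjusts for centre with a pooling rule, and Section 1.6 ranks randomisation protocol first in order to keep comparisons concurrent. A reader might infer that the SAP ignores site. It does not. What remains is that the only centre-adjusted results are secondary in status. The concurrency argument is also weak for B against C, because their allocation is 1:1 under every version. Stage 1 is an imperfect precedent, since it had no protocol-version factor and stratified by HIV status only where co-infection was common.
- **Adding site can backfire.** With cells under 10 pooled within regions, a fully crossed analysis still widened the mean standard error in five of six simulated settings (for example 0.0425 to 0.0438 with 15 sites and s = 0). This is right about full crossing and shapes the fix. It does not apply to a pooled-site or additive analysis.

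**Conclusion.** The mismatch between the randomisation factors and the primary analysis is real. Its consequence is conditional and small. If site predicts outcome, the primary interval is modestly conservative: the standard error is about 0%, 0.8% or 3.4% too wide at an assumed between-site standard deviation of 0, 5 or 10 points. At 10 points that is 8.29 − 8.01 = 0.28 points of half-width and 83.5 − 81.8 = 1.7 points of power.

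It would be tempting to say flatly that the standard error is too wide, but the documents contain no figure that establishes it. Omitting site does not inflate type I error and does not leave the trial short of its planned power.

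The sizes rest on the assumed spread, exact balance within site, the planning rates, and 172 evaluable patients per arm. They are upper figures for the gain, because the formula treats adjustment as free.

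**What to change.** **If the Week 76 analysis has not been run,** bring sensitivity B's pooled site grouping into the primary analysis in one of two ways, neither of which crosses site, protocol version and HIV status fully:

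- stratify the Mantel-Haenszel risk difference by pooled site and HIV status, merging the two HIV-positive groups where data are sparse. Leaving protocol version out of the strata is safe for this comparison because B:C allocation is 1:1 throughout; or
- adjust additively for pooled site, HIV status and randomisation protocol on the risk-difference scale.

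State where site falls in the Section 1.6 collapsing order, and keep the present protocol-and-HIV analysis as a sensitivity analysis.

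**If it has been run,** as the past-tense wording in SAP Sections 6.1.3 and 7.1 suggests, do not replace the primary model. Report sensitivity B beside the primary result and note that the primary interval is expected to be conservative if outcomes vary by site.

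**Cost:** a few sentences in the SAP. A few patients in one-arm strata may be lost under the first option, and there is no gain if site does not predict outcome.

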6.2 Tabulation of primary endpoint classification

Since the primary endpoint is a composite of various components, the actual reason (component) for outcome will also be tabulated by treatment arm. Patients will be classified by the first event that made the patient unfavourable (see section 3.2) and further subclassified by whether their outcome is deemed to be bacteriologically related or not, based on a review of all data up to the time that the outcome occurred (see Section 6.2.1).

6.3 **Subgroup analyses**

This primary efficacy analysis will be repeated (in both mITT and PP analysis populations) in subgroups according to the following baseline characteristics:

- HIV infection status
- baseline drug resistance patterns (i.e. resistance to pyrazinamide and isoniazid)
- albumin levels (by severity grade)
- BMI (<16.0 kg/m², 16.0-18.4 kg/m², 18.5-24.9 kg/m², >25 kg/m²)
- cavitation (presence, absence)
- study centre/country
- age (<25, 25-<45, ≥45)

- sex
- Smoking history (current, ex, never)
- Smear grade
- Weight band (<33kg, 33-50kg, >50kg)
- Race.

6.4 **Sensitivity analyses**

The primary efficacy analysis will be repeated:

- A. Unadjusted for any covariates except randomisation protocol.
- B. Adjusted for randomisation stratification factors HIV status and centre. Small strata with fewer than 10 patients will be combined within geographical regions within country.
- C. Adjusted for randomisation stratification factors and any additional important covariate such as cavitation at baseline, baseline bacillary load or adherence.
- D. Ignoring substitutions of levofloxacin for moxifloxicin and vice versa when counting the number of drug substitutions within the definition of unfavourable outcome.
- E. Ignoring starting linezolid alone as a criterion for an unfavourable outcome.
- F. Reclassifying any participants with reinfection (based on genotype or DST) as "non-assessable" rather than unfavourable.
- G. Reclassifying any participants who died as a result of trauma (as adjudicated by independent review) as "non-assessable" rather than unfavourable.
- H. Reclassifying any participants with missing Week 76 culture results because of COVID-19 as "non-assessable" rather than unfavourable.
- Reclassifying any participants with missing Week 76 culture results because of COVID-19 as favourable if they meet the definition of favourable, with the latest of the 2 negative culture results being within the Week 68 window, unfavourable otherwise.
- J. Requiring a 25 day delay between the last 2 negative culture results in participants classified as favourable. A participant's outcome will be unfavourable if previously classified as favourable but not meeting this definition. . .
- K. In the ITT analysis population
- L. In the safety analysis population

Analyses D to J will be repeated adjusted only for randomisation protocol.

6.5 **Bayesian analysis of non-inferiority**

An exploratory Bayesian analysis of non-inferiority provides an estimate of the probability that Regimen B has efficacy not much worse than Regimen C for different thresholds of what might be considered 'not much worse'.

Following methods described previously⁶, we will use Bayesian binomial regression to estimate the distribution of the (unadjusted) difference in the proportion of favourable outcomes between regimens B and C. Gaussian Normal priors will be placed on the intercept term (mean = 0.0 and variance = 100) and on the difference in proportion between regimens (Flat: mean = 0.0 and variance = 100, Sceptical: mean = 0.02 and variance 0.05, and Expected: mean = -0.02 and variance 0.05). The Flat prior is an uninformative prior

with very large variance centred around zero representing weak prior information, the Sceptical prior is centred around an absolute 2% increase in proportion of favourable in Regimen B with a smaller variance, and the Expected prior represents the assumptions used in the sample size calculations representing an absolute 2% increase in the proportion of favourable outcomes in regimen C. Initial values for the Markov Chain Monte Carlo algorithm came from estimates from the frequentist binomial regression model. This analysis will be on the mITT population.

